# 1. PROTOCOL SUMMARY

[figure not shown]
## 1.1. Synopsis

Title:	Traumatic Nightmares Treated by NightWare (To Arouse Not Awaken): A Randomized Controlled Trial
Study Description:	
This is a double-blinded, sham-controlled, randomized controlled trial to establish the safety and efficacy of the NightWare (NW) digital therapeutic system (NW System) which is to be used for the treatment of sleep disturbances related to nightmares associated with post-traumatic stress disorder (PTSD). This system consists of a Smartphone, a Smartwatch, and a proprietary application. This study will compare the Active System, which monitors sleep and provides tactile stimulation to terminate nightmares, to the Sham System that while it does monitor sleep, does NOT provide intervention but is otherwise identical. This study seeks to determine the safety and efficacy in treating PTSD-related sleep disturbance with the NW System as well as delineating the impact of improved sleep when using the Active System versus the Sham System.
 
The investigators hypothesize that the Active System will significantly improve sleep quality in subjects with PTSD-related sleep disorders who are suffering from nightmares and poor sleep quality, and that the magnitude of improvement will be greater than that observed in the subjects who receive a Sham System.

Objectives:	
Primary Objectives:
 
 
● Demonstrate that the Active System improves sleep quality as assessed by the Pittsburgh Sleep Quality Index (PSQI) in participants with PTSD
 
● Demonstrate that improvement in sleep quality is greater for the Active System than the Sham System
 
● Demonstrate that the Active System does not lead to worsening of daytime sleepiness as assessed by the Epworth Sleepiness Scale (ESS)
 
● Demonstrate that there is not an increase in suicide risk as assessed by the Columbia-Suicide Severity Rating Scale (C-SSRS)
 
 
Secondary Objectives:
 
 
● Evaluate changes in the following measures between Day 0 (baseline) and Day 30: 
 
- PTSD severity [PTSD Checklist (PCL-5)]
 
- Sleep quality [PSQI Addendum for PTSD (PSQI-A)]
 
- Subjective sleep quality [NW Likert Scale for Sleep Quality]
 
- Quality of life [Functional Outcomes of Sleep Questionnaire (FOSQ-10) and Veterans Rand 12 Quality of Life instrument (VR-12)]
 
- Nightmare severity/frequency [TRNS]
 
- Depression symptoms [Patient Health Questionnaire-9 (PHQ-9)]
 
 
 

	- Insomnia Severity Index (ISI)
Outcomes:	
Primary Efficacy Outcomes:
 
 
● Difference between PSQI score at baseline (Day 0) and average PSQI score at the post-treatment assessment (Day 30) [i.e., PSQI change] in the Active System.
 
● Difference in average PSQI change scores between Active System and Sham System conditions.
 
 
Primary Safety Outcomes:
 
 
● No significant increase in ESS between baseline (Day 0) and Day 30 in the Active System.
 
● No increase in C-SSRS severity score between Day 0 and Day 30 in the Active System.
 
 
Observational Outcomes:
 
 
● Improvement in sleep quality, nightmare frequency/intensity, quality of life, PTSD severity, and depression symptoms between Day 0 and Day 30 in the Active System.
 
● Greater improvement in sleep quality, nightmare frequency/intensity, quality of life, PTSD severity, and depression symptoms in the Active System relative to the Sham System.
 

Study Population:	480 potential participants will be screened and 240 adults (120 in each arm), equal to or over the age of 22 years with symptoms indicative of PTSD and related nightmares will be enrolled into the study protocol. This is a multi-site study and will include active-duty military members, military veterans, and military family members.
Planned Number of Sites:	This study will be conducted at WRNMMC and FBCH as the two DoD sites. It is also conducted at multiple VA Hospitals.
Description of Study Intervention:	Wearable digital therapeutic system that will measure physiologic data when worn during sleep to deliver a mild vibration via the watch (i.e., haptic feedback) to elicit an arousal thereby disrupting nightmares. This detection and stimulation sequence will be performed according to NW's proprietary algorithm.
Participant Duration:	30 days in a randomized control trial followed by an additional 60-day open label extension.
Data Banking	De-identified data generated from this study will be saved for use in future studies. The site will transfer data to NightWare that does not contain individual identifiable information.

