## 7.2. Statistical Hypothesis Testing

The primary hypothesis is that NW will improve sleep quality as measured by the Pittsburgh Sleep Quality index (PSQI) relative to sham. On average, compared to the sham, NW will provide a greater reduction in PSQI score measured on day 30 relative to baseline on day 0

Let  $Y_{ij}$  denote the PSQI score for the  $i$ -th participant at their  $j$ -th assessment,  $j=0,1,2$ , where  $j=0$  denotes baseline, and  $i=1,\dots,n$ . Let  $D_i = Y_{i0} - Y_{i1}/2$ , i.e., the difference between the  $i$ -th participant's PSQI score at baseline ( $Y_{i0}$ ) and their average PSQI score across the post-treatment initiation assessment ( $Y_{i1}$ ). The trial will test the hypotheses

$$H_0: \mu_{\text{Active}} \leq \mu_{\text{Sham}} \text{ versus } H_A: \mu_{\text{Active}} > \mu_{\text{Sham}},$$

where  $\mu_{\text{Active}}$  and  $\mu_{\text{Sham}}$  respectively reflect the average difference with NW and sham.

We will evaluate the statistical hypotheses using an equal-variances, two sample t-test. If the equal variance assumption is untenable, we instead will use an unequal-variances, two sample t-test, i.e., Welch's t-test. We will reject the null hypothesis ( $H_0$ ) that change in PSQI from baseline to day 30 resulting from the active NW system is no better than sham when the two-sided p-value is less than or

equal to 0.05 and the direction of the difference favors NW over sham. In this way, the proposed test controls the one-sided type I error rate at 2.5%.

Data will be presented as mean(standard deviation) or median (interquartile range), as appropriate for continuous variables. Categorical variables will be presented as frequency (percentage). Continuous data will be assessed for normality, and transformed as appropriate (e.g. log transformation, square root transformation, etc.). Patient demographics and characteristics will be listed and compared.

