### 7.3. Sample Size Determination

A total of 240 veterans and active-duty service members will be enrolled (consented) into the study so that even with attrition of up to 50% of study subjects, we can ensure that the study is completed by a MINIMUM of  $n = 120$  participants (60 in each arm) to reach 90% power for rejecting the null hypothesis under the targeted benefit of  $\delta = \mu_{\text{Active}} - \mu_{\text{Sham}} = 3$  points with an equal standard deviation of  $\sigma = 5$  points in each of the two arms. Figure 1 (see below) depicts the power of the trial as a function of the true standardized reduction ( $\delta/\sigma$ ) in the population assuming we enroll and **retain** a MINIMUM of 60 participants in each arm of the proposed trial. If we get more than 60 participants (i.e. less than a 50% attrition rate) this will just make the study results even more powerful.

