**Figure 4: Power Curve (total completers-  $n=120$ , 50% for each arm)**

The rationale for powering the trial to detect a 3-point reduction is two-fold. First, a 3-point reduction constitutes a clinically relevant benefit as this may reflect, for example, a change from 3 (most severe) to 0 (least severe) on a particular item of the PSQI, or a 1-point reduction on three items of the PSQI. Second, assuming a 5-point standard deviation, the targeted 3-point reduction is equivalent to a 0.6 standardized effect, which is plausible as evidenced by a meta-analysis for the observed benefit in previous clinical trials evaluating cognitive behavioral therapies for treating nightmare disorder using the difference between PSQI score at baseline and post-treatment follow-up assessment in which the estimated standard effect size was estimated to be 0.68 (0.34, 1.03). Furthermore, a more recent open-label trial reported a standardized effect size of 1.06. Therefore, the targeted 3-point reduction or 0.6 standardized effect constitutes both a plausible and clinically meaningful benefit in this context.

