#### **7.5. Primary Safety Analyses**

The hypothesis for the primary safety endpoint is that the Active NW System will not lead to worsening of daytime sleepiness as measured by the Epworth Sleepiness Scale, which provides a score between 0 and 24 with higher values indicating a higher degree of sleepiness. Specifically, the hypothesis is that on-average a user of NW will have a mean ESS score measured at 30 days following the start of NW digital therapeutic system use that is not higher than their ESS score measured at baseline. This hypothesis will be tested similarly to the primary efficacy hypothesis using a one sample t-test.

The hypothesis for the secondary safety endpoint is that the Active NW System will not lead to an increase in suicide risk as assessed by Columbia-Suicide Severity Rating Scale (C-SSRS) from baseline (Day 0) to Day 30. C-SSRS has ratings of "none", "low", "moderate", and "high". Those possible participants rated as "high" on the C-SSRS at Visit 1 will NOT qualify for the study and, if deemed necessary by the PI, will be given immediate assessment by a licensed Mental Health Provider, who will determine the next therapeutic steps. This hypothesis will be tested similarly to the primary efficacy hypothesis using a one sample t-test.

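### The primary ESS safety criterion counts a non-significant pre/post test in the Active arm as showing no worsening, with no margin and without using the sham arm

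*Protocol*

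**What the plan says.** The Protocol Synopsis (1.1) lists this among the primary objectives: "Demonstrate that the Active System does not lead to worsening of daytime sleepiness as assessed by the Epworth Sleepiness Scale (ESS". The matching primary safety outcome is "No significant increase in ESS between baseline (Day 0) and Day 30 in the Active System".

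Protocol 7.5 states the hypothesis as a mean Day 30 ESS "that is not higher than their ESS score measured at baseline", and gives the method: "This hypothesis will be tested similarly to the primary efficacy hypothesis using a one sample t-test". The SAP repeats both under Primary Safety Analyses. All that either document says about the scale is that it "provides a score between 0 and 24 with higher values indicating a higher degree of sleepiness". Neither gives a margin, a confidence-limit rule, an SD for ESS change or a power statement for ESS.

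The only sample-size argument (7.3) is for PSQI: "60 in each arm) to reach 90% power for rejecting the null hypothesis".

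The Schedule of Activities (1.3) collects ESS at Day 0 and Day 30 with no restriction by arm, so sham ESS data will exist.

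**The concern.** An objective worded as a demonstration needs a result that excludes a worsening of some stated size. A non-significant test excludes nothing in particular: it can come from a harmless device or from too few observations. Under this rule, attrition or an early stop makes the safety claim easier to obtain.

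The second weakness is the missing control. Participants must score 10 or more on the PSQI to enter (5.1), so some improvement unrelated to the device is plausible over 30 days. In a pre/post test within the Active arm, that improvement cancels a device-related increase in sleepiness of the same size. The randomised sham arm would show the increase, but the primary criterion does not consult it.

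This matters because worsened sleep is the risk the protocol itself names (9.1.1: the device may wake the user or react to a false positive), and 9.1.3 names the ESS as the endpoint that is to detect it.

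**Working it through.** **The plan's own figure.** For PSQI, δ = 3, σ = 5, 60 per arm, two-sided 0.05 (7.2, 7.3): noncentrality = (3/5)·√(60/2) = 3.286 on 118 df, power 90.3%. The stated 90% reproduces, and 120/(1 − 0.5) = 240 enrolled also follows. This calculation is sound, but it was not made for ESS.

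**Inputs for ESS.**
- Level: 7.2 says that "the proposed test controls the one-sided type I error rate at 2.5" per cent, and ESS is to be tested similarly, so an increase is declared at upper one-sided 0.025.
- Active completers n: 120 with full retention; 60 as the planned minimum (7.3); about 20 only if the trial stops at the first interim look (7.4).
- SD of ESS change: not in the documents. Assumed 4 to 5 points, with 3 as a check.
- True mean worsening d: assumed 1 or 2 points.

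**Probability that the present rule passes.** P(pass) = F(t₀.₉₇₅,ₙ₋₁), where F is the noncentral t distribution with n − 1 df and noncentrality d·√n/σ. Example: n = 60, d = 1, σ = 4 gives noncentrality 1·√60/4 = 1.936, critical value 2.001, P(pass) = 52.2%.

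| True worsening | SD | n = 20 (early stop only) | n = 60 | n = 120 |
|---|---|---|---|---|
| 1 point | 3 | 70.7% | 28.1% | 4.8% |
| 1 point | 4 | 81.5% | 52.2% | 22.5% |
| 1 point | 5 | 86.7% | 66.9% | 41.6% |
| 2 points | 4 | 43.6% | 3.2% | <0.1% |
| 2 points | 5 | 60.3% | 13.8% | 0.9% |

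In every row the pass rate rises as n falls. At one-sided 0.05, the 1-point rates for SD 4 and 5 are 39.4% and 54.5% at n = 60, and 14.0% and 29.7% at n = 120.

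**Non-specific improvement.** Device effect +1 and general improvement −1 give a net Active change of 0. The noncentrality is then 0 and P(pass) = 97.5% at every n, although Active is 1 point worse than Sham.

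**A between-arm rule with margin m.** The rule passes if the upper 95% limit of Active − Sham is below m. P(pass) = 1 − F(t₀.₉₇₅,₂ₙ₋₂), with 2n − 2 df and noncentrality (m − d)/(σ·√(2/n)). Example: n = 60 per arm, m = 2, d = 0, σ = 4 gives SE = 4·√(2/60) = 0.730, noncentrality 2.739, P(pass) = 78%.

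| Per arm | Margin | True difference | SD 4 | SD 5 |
|---|---|---|---|---|
| 60 | 2 | 0 | 78% | 58% |
| 60 | 3 | 0 | 98% | 90% |
| 120 | 2 | 0 | 97% | 87% |
| 60 | 2 | 1 | 27% | 19% |
| 60 | 3 | 1 | 78% | 58% |

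The margins only illustrate the calculation; the documents support none. The SD is taken as that of the unadjusted change, and adjustment for baseline would raise the power somewhat.

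**The case against.** Four stronger readings are tempting, and the documents do not support them.

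- *The sham arm is never used for ESS.* Protocol 7.6 and the matching SAP text plan a repeated-measures comparison between groups covering every survey, and intervention-versus-control tests for continuous variables. A sham comparison of ESS is therefore foreseeable. However, it is secondary or exploratory, applies only where judged appropriate, has no margin and does not decide the safety claim. The accurate statement is that the primary criterion does not use sham.
- *The test contradicts its own description, because the efficacy test it is modelled on has two samples.* That is true only of 7.2. The Synopsis also lists the within-Active PSQI change as a primary efficacy outcome, and a one-sample ESS test parallels it. At most the wording is ambiguous.
- *The safety claim will rest on 20 participants.* The plan aims for at least 60 completers per arm. ESS is not analysed at the interim looks, and about 20 would remain only after crossing an O'Brien-Fleming boundary at the first look, which is a strict one.
- *The test could not detect any harm.* With 60 completers and no offsetting improvement, a 2-point worsening is missed only 3–14% of the time.

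One objection bears on the remedy: a wide margin can be no stricter than the present rule. With 3 points and 60 per arm, a true 1-point Active–Sham worsening still passes 58–78% of the time, against 52–67% now. This stands. The gain lies in the randomised control and in no longer rewarding small samples; strictness depends on the margin chosen.

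**Conclusion.** Wrong as written. The criterion does not match the objective: non-significance in one arm cannot demonstrate that worsening is absent, and nothing states what size of worsening must be excluded. The weakness is greatest for a worsening of about 1 point, where the pass rate is 52–67% at the planned minimum and 22–42% with full retention, and wherever general improvement offsets a device effect (about 97.5% at any n).

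These rates rest on an assumed SD of 4 to 5 points; at SD 3 the 1-point pass rate at 60 completers falls to 28%. Two conclusions hold whatever the SD: fewer completers make a real worsening easier to pass, and a within-arm test cannot separate device effect from general change. The PSQI sample size is not in question.

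**What to change.** In the Synopsis, Protocol 7.5 and the SAP:

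1. Make the primary ESS analysis the Active–Sham difference in Day 30 ESS, adjusted for baseline ESS, with a two-sided 95% CI.
2. Conclude no worsening only if the upper limit lies below a margin that is justified in the protocol and fixed before any unblinding.
3. Report the within-Active change descriptively.
4. If no margin can be agreed, report the between-arm estimate with its CI and drop the claim that absence of worsening was demonstrated.

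Replacing the one-sample test with a two-sample significance test is not enough. With 60 per arm it would detect a 1-point difference only 19–27% of the time (SD 5 to 4), and non-significance would still count as success.

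The cost is wording and agreement on one margin; no new data are needed. The price is a claim that is harder to meet. With no true difference and SD 4 to 5, power at 60 per arm is 58–78% for a 2-point margin and 90–98% for 3 points; at 120 per arm it is 87–97% for 2 points. The justification of the margin should state which true worsening it would still let through.

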## 1.2. Schematic

### 1.3. Schedule of Activities

Study Activities Table:

Study Activity	Pre-Tx	Visit 1	Calibration	Start Up Call	Help Calls	Check Up Call 1	Assessment Call	Check Up Call 2	Visit 2	Visit 3	Visit 4
Study Day	Before Day 0	Day 0	Days 0-3	Day 1	Days 2-6 (Optional)	Day 7	Day 14 (+/-3)	Day 21 (+/- 2)	Day 30 (+/- 7)	Day 60 (+/- 7)	Day 90 (+/- 7)
Recruitment	X										
Chart Review	X										
Phone Screen	X										
Inclusion/Exclusion	X	X									
ICF and HIPAA		X									
Modified Dysken I		X a									
AUDIT		X b									
DAST-10		X c									
Demographics		X									
Medical History		X									
Blood Pressure		X							X		
Med Reconciliation		X							X	X	X
PSQI		X					X		X	X	X
PSQI-A		X							X		
ESS		X							X	X	X
ISI		X							X	X	X
PCL-5		X					X		X	X	X
CAPS-5		X									
VR-12 (QOL)		X							X	X	X
TRNS		X							X	X	X

FOSQ-10		X							X		
PHQ-9		X					X		X	X	X
C-SSRS Lifetime		X							X	X	X
Blinding Assessment Questionnaire									X		
NW Likert Scale		X							X	X	X
Daily Use Questionnaire (Days 1-90)				X	X	X	X	X	X	X	X
Calculate Cutoffs/Eligible ?		X									
Dispense NW Devices		X									
Train Subject		X									
Activate Devices		X									
C-SSRS Since Last Contact									X	X	X
Payment of Subject(Bi weekly)	See Reimbursement Section 6.15										
Start Up Call				X							
Calibration			X								
Active/Sham Treatment			Post- Calib. f								
Help Calls Questionnaire (Optional)					X	X		X			
Checkup Phone Call						X		X			
Sham Cross- over to Active Treatment									X		

a—Administered DURING informed consent process to ensure subjects are capable of consent. Subjects must get all responses correct to be enrolled into the study, b-Exclude if score is equal to or greater than 8. c-Exclude if score is greater than 2. f-Only the Active System goes through calibration and on to Active Treatment.

## 2. INTRODUCTION

### 2.1. Study Rationale

Nightmares are a common problem affecting around 2-8% of the general population and a higher proportion of clinical populations. The negative consequences of untreated nightmares are significant and include impaired quality of life, sleep deprivation (often resulting in increased intensity of nightmares), insomnia, daytime sleepiness, and fatigue. Untreated nightmares can also exacerbate the symptoms of underlying psychological dysfunction in subjects with depression and anxiety, leading to poor occupational and or social functioning.

Nightmares can be idiopathic or associated with the use (or withdrawal) of certain medications/substances, or associated with disorders including PTSD.

While nightmares are readily observed and recognized by subjects and their family members, nightmare physiology is still poorly understood. Despite a limited understanding of the mechanisms of nightmares, there are treatments that show variable efficacy. The American Academy of Sleep Medicine makes two recommendations for the treatment of nightmare disorder. One is pharmacological and the other is non-pharmacological.

**Prazosin**, an alpha 1 antagonist antihypertensive, is a medication routinely used to treat nightmares and it is thought to mediate its effects by reducing the sympathetic outflow in the brain during sleep. While there has been evidence to support its efficacy in treatment of nightmares, common side effects include orthostatic hypotension and rebound hypertension with missed doses. Its interaction profile with other medications also limits use in clinical populations.

**Image Rehearsal Therapy**, a modified cognitive behavioral therapy technique, is a non-pharmacological approach that appears to be effective. It requires the subject to write down the nightmares and THEN rehearse those nightmares (inserting a positive result) prior to sleep. However, studies demonstrate poor compliance with therapy. Moreover, rehearsing the nightmares immediately prior to bed carries the risk of re-exposing the subject to their traumatic nightmare and, thus, exacerbating the symptoms of nightmares as well as increasing the frequency of nightmares.

NightWare (Minneapolis, MN) has developed a novel approach to the treatment of nightmares. Through the use of a smartwatch-based application that senses physiologic parameters, the patient is aroused from sleep (without awakening the patient) so that the nightmare is interrupted prior to reaching a threshold of severity in which the patient would awaken in distress. Seconds later the patient returns to sleep without having experienced a nightmare. This approach avoids risk from pharmacological treatment, avoids exacerbation of symptoms from image rehearsal therapy and allows for a simple method with easily achieved adherence compared to existing treatments.

## 2.2. Background

Approximately 80% of subjects with PTSD have nightmares that begin within the first 3 months of the trauma. Although up to 50% of subjects with PTSD have resolution of their nightmares within 3 months, a substantial proportion experience lifelong nightmares.

Despite their prevalence and distress, nightmares are frequently underreported and thereby undertreated. In a study published in 2015, more than 60% of subjects did not discuss clinically significant nightmares with their healthcare professional.

Trauma related nightmares and accompanied sleep disturbances are thought to contribute to the development of PTSD as well as worsening symptom severity, functional impairment, distress and overall poor quality of life.

Nightmares are categorized by whether they are due to a medication or substance, associated with a psychiatric disorder such as PTSD, or idiopathic, meaning the cause is not readily known.

The diagnosis of nightmares is made by a clinical history and examination. Laboratory tests are not routine unless there is suspicion for a drug use disorder.

Sleep diagnostic testing using Polysomnography is not indicated for the diagnosis of nightmares, as nightmares tend to occur less frequently in a clinical sleep laboratory setting. This is presumed to be due to the “first night effect” in which subjects’ sleep architecture may be different than in their natural home sleep environment.

